
Any research staff member who learns of an adverse event is responsible for reporting the event to the Principal Investigators (PI), who are in turn responsible for discussing the event to make a joint decision about whether the event is serious or non-serious. Events will be categorized as adverse or serious adverse according to NIH guidelines: "Adverse events (AEs) are defined as any untoward medical occurrence that may present itself during treatment or administration of an intervention, and which may or may not have a causal relationship with the treatment. Serious adverse events (SAEs) are defined as any medical occurrence that results in death; is life-threatening; requires inpatient hospitalization or prolongation of existing hospitalization; creates persistent or significant disability/incapacity, or a congenital anomaly/birth defects." As such, adverse events (AEs) occurring during the course of the study will be collected, documented, and reported to the PIs. Each week a study investigator will review the AE Forms from the previous week for events that were reported as new or continuing.
	

Any SAE will be reported to the IRB within 48 hours of the occurrence. The report of SAEs will include whether they were expected or unexpected, a rating of severity of the event, a brief narrative summary of the event, a determination of whether a causal relationship existed between the study procedures
	

and the event, whether the informed consent should be changed as a result of the event and whether all enrolled participants should be notified of the event. Finally, as part of the annual progress report (noncompeting continuation application) to NIH, we would provide summary information on all SAEs that have occurred during that year.

Any actions taken by the IRB will be reported promptly to NIH via the Project Officer or appropriate parties.

Additionally, the PIs and [name] will closely monitor the validity and integrity of the data on an ongoing basis. The DSMB will also conduct biannual monitoring of the data through spot checks and independent preliminary analysis of the data. For instance, the PIs and the project staff will meet regularly with project interviewers to review assessments and coding of incoming data. The PIs will be responsible for ensuring that data are being coded, entered and cleaned appropriately. The full research team will meet every week for 120 minutes to review all aspects of the research study.

8E. If subjects will be recruited from Illinois public or private elementary or secondary schools, additional deadlines and procedures may apply. Criminal background clearances might be required. Special consideration must be given to the exclusion of protected populations. Please contact the [School University Research Relations \([contact]\)](mailto:[contact]) for more information. Select one: Illinois schools will be used Illinois schools will not be used

Section 9. SUBJECT ENROLLMENT GOAL & EQUITABLE SELECTION OF SUBJECTS

9A. For each performance site, indicate the estimated total number of participants.

Performance Site	# Male	# Female	Total
#1 CBHC	252	295	548
#2 NJCRI (oversight by NJCRI IRB)	328	341	670
#3 UM	0	0	0
TOTALS	580	636	1218

If additional performance sites are included on an attachment, check here:

9B. Select all participant populations that will be recruited.

Age:

Adults (18+ years old)

Minors (≤17 years old)

Specific age range, *please specify*:

Gender:

No targeted gender (both men and women will be recruited/included)

Targeted gender, *please indicate*: Men/boys Women/girls Other, *please specify*:

Race/Ethnicity:

No targeted race or ethnicity (all races and ethnicities will be recruited/included)

Targeted race or ethnicity, *please specify*:

College Students:

- No targeted college population
- UIUC general student body
- Targeted UIUC student population, *provide the instructor or course information, name of the departmental subject pool, or other specific characteristics:*
- Students at institution(s) other than UIUC, *please specify:*

Any research with students on UIUC's campus needs to be registered with the [Office of the Dean of Students](#).

Other:

- Inpatients
- Outpatients
- People who are illiterate or educationally disadvantaged
- People who are low-income or economically disadvantaged
- People with mental or cognitive disabilities or otherwise impaired decision-making capacities
- Adults with legal guardians
- People who are non-English speaking
- People with physical disabilities
- Pregnant or lactating women, human fetuses, and/or neonates
- Prisoners or people with otherwise limited civil freedoms
- Other, *please specify:* target population faces disproportionate COVID-19 risks due to employment as essential workers, poverty, inadequate or unstable housing, and underlying medical conditions.

9C. Describe additional safeguards included in the protocol to protect the rights and welfare of the populations selected above.

To avoid possible violations of confidentiality, project staff are trained to carefully follow detailed procedures designed to assure that no information about any participant (or others they may mention) will be given to law enforcement, other government agencies, or anyone but research staff. Every member of the research team and all members of the NCCB and the Illinois Community Collaborative Board (ICCB) will be required to undergo human subject protection training and provide a certificate of completion to the

IRB prior to any contact with human subjects. Standards of confidentiality include the use of code numbers and code names for participants and other individuals they may mention. The only place participants' names or other identifying information will appear is on informed consent forms and locator forms (used for follow-up interviews after the baseline). These forms will be kept electronically in REDCAP, in a folder separate from the data. Only full time, trained staff in the project including the outreach works, project coordinator, research assistant, and PIs will have access to these files. Peer navigators will not have access to data from the individuals that are randomized into their groups. They will receive a report from RedCAP highlighting any reported risk for COVID-19 exposure that they will be discussing with the participant during the navigation.

The electronic files generated through data collection will be identified by code numbers and

codenames only and kept in password-protected devices/servers, separate from identifying information and available only to project staff. This helps to ensure that no identifying information will be disclosed in the unlikely event that computerized data are stolen or otherwise seen by unauthorized persons.) All identifying electronic data will be destroyed immediately after data analysis is completed. Signed consent forms will be kept for 3 years after study completion. Deidentified electronic data will be kept indefinitely. Participants may ask at any time to have recordings of their interview destroyed by calling/e-mailing one of the Principal Investigators at the numbers provided in the informed consent forms. Voice recordings will be kept indefinitely for data analysis. However, if we have reason to believe that any of these recordings contain information that can put any of our participants in danger of being harmed, we will destroy the recording.

Our interviewers are trained to watch participants carefully and will stop questioning if an individual appears uneasy. At every interview, participants will be informed that they may ask the interviewer to stop if they are feeling uncomfortable. Referrals to counselors are available if participants wish and trained clinical counselors are available at CHBC in the event that someone may need immediate assistance, whether it is during data collection or during the intervention sessions. [name], [name], and [name] will be available by phone at all times in case an emergency occurs. Clinical emergencies will be handled by treatment teams of experienced staff at CBCH under the leadership of [name]. Appropriate assessments will be conducted; treatment options will be recommended and followed through as necessary. CBHC routinely provides services to individuals with mental health and substance use disorders is fully equipped to address any potential emergencies either themselves or via referrals.

Finally, the research team and the clinical team will engage in weekly project meetings to discuss the progress of the study and identify, discuss, and address any potential issues.

Section 10. INCLUSION/EXCLUSION

10A. List specific criteria for inclusion and exclusion of subjects in the study, including treatment and control groups.

Criteria for inclusion include:

- 18 years of age or older
- having high risk to contract COVID-19 or develop related complications
- able to Speak English at the 7th grade level
- able and willing to provide informed consent

10B. Explain how the inclusion/exclusion criteria will be assessed and by whom. If special expertise is required to evaluate screening responses or data, list who will make this evaluation and describe their training and experience.

A trained outreach worker will conduct a brief phone screening using the attached brief phone screening to obtain self-reported eligibility information including risk for contracting COVID-19 and developing related complications.

10C. Drafts or final copies of all screening materials are attached. Yes Not Applicable

10D. Describe procedures to assure equitable selection of subjects. Justify the use of the groups marked in Section 9B. Selection criteria that target one sex, race, or ethnic group require a clear scientific rationale.

The proposed study does not include children because the adaptive intervention will focus on adult behaviors and it would not be appropriate to include children. The staff has been trained to work with adults and the parent grant only included individuals over the age of 18. Finally, the supplement includes several interview questions regarding social determinants of health that children would not be able to answer. Recruitment will be open to residents of both Essex County, NJ and St. Clair County, IL, but given the location of the study sites, we expect that the vast majority of participants will come from the Newark, NJ and East St. Louis, IL areas. As such, we estimate that our sample will approximate the demographics of Newark and East St. Louis in terms of sex/gender, race and ethnicity. Because of this, we anticipate that Black participants will be overrepresented in our sample.

Section 11. RECRUITMENT

11A. Select all recruitment procedures that will be used.

- Student subject pool, *please specify*:
- Email distribution
- MTurk, Qualtrics Panel, or similar online population, *please specify*:
- US Mail
- Flyers/brochures
- Website ad, online announcement (e.g. eWeek), or other online recruitment, *please specify*:
- Newspaper ad
- Verbal announcement
- Other, *please specify*: Street outreach
- Not applicable (secondary data only)

11B. Drafts or final copies of all recruitment materials (including verbal scripts) are attached.

- Yes Not Applicable

11C. For each group of participants, describe the details of the recruitment process.

We will enroll a sample of 548 in St. Clair County. The ICCB and outreach staff will post fliers at bus stops, health care agencies, churches, bulletin boards, and social service agencies, giving consideration to the demographic characteristics of those agencies' clients and of neighborhoods. Individual service providers and potential participants will be asked to share the study's fliers in their neighborhoods, churches and other meeting places. Those who are interested will call the study phone number that is listed on the flyer. Street outreach will be used following social distancing protocol. All consenting CBHC clients will be screened and those eligible will be invited to participate in the study. People interested in participating will call the study's cell phone number. A trained outreach worker will conduct a brief phone screening using the same brief phone screening that is currently being used in the Essex County, NJ to obtain self-

reported eligibility information including risk for contracting COVID-19 and developing related complications.

Section 12. REMUNERATION AND PLAN FOR DISTRIBUTION

Refer to the University [Business and Financial Policies and Procedures](#) for further guidance on the compensation process and reporting requirements.

12A. Will subjects receive inducements or rewards before, during, or after participation?

Yes No

If yes, complete the rest of Section 12. If no, proceed to Section 13.

12B. Select all forms of remuneration that apply.

Cash, *please specify amount*: \$30 for baseline, \$40 per follow up, \$30 for group session, and \$50 for the exit interview for a maximum possible of \$270 per individual

Check, *please specify amount*:

Gift Certificate, *please specify amount*:

Lottery, *please specify amount*: *and odds*:

Course Credit, *please specify amount*: *and specify equivalent alternative activity*:

Other, *please specify*:

12C. Will payment be prorated before, during, or after participation?

Yes, *please specify how*: Payments will be received after completion of each survey during the study.

No

12D. For each group of participants, describe the details of the remuneration plan, including how, when and by whom they will be notified.

Participants will receive modest cash incentives for taking part in data collection activities. Each participant will receive \$30 for completing the baseline assessment. Each participant will receive \$40 per each of the four “follow up” visits. Each participant will receive \$30 for attending a one hour Critical Dialogue session. The maximum amount possible for participation is \$270 per individual.

12E. The information listed above is provided on the relevant consent forms.

Yes

Section 13. RISKS & BENEFITS

13A. Describe all known risks to the participants for the activities proposed, such as risks to the participants' physical well-being, privacy, dignity, self-respect, psyche, emotions, reputation, employability, and criminal and legal status. Risks must be described on consent forms.

The main potential risks of this study include inadvertent violation of confidentiality and emotional distress on the part of participants. The use of code names and numbers along with other procedures described below are intended to prevent violations of confidentiality. It is important to be aware that the prospect of testing positive for COVID-19 may be a cause of substantial fear and anxiety among

participants. We anticipate that more than half of our participants will be African American or Hispanic and may lack trust in medical science and practice as a legacy of medical mistreatment. Many participants will have lost loved ones to COVID-19 and all of them will be medically or socially vulnerable to poor outcomes if they become infected themselves. They live with disproportionate risk caused by any of several factors, including but not limited to employment as essential workers, poverty, inadequate or unstable housing and underlying medical conditions. CBHC has been operating as a primary provider of services in East St. Louis, IL for 50 years. It is, in general, a trusted source of care and services, but the COVID-19 pandemic is a recent, evolving development and much remains unknown about community perceptions.

It is also possible that participants who decline testing and attend Critical Dialogue sessions may be disturbed by sensitive questions raised during those sessions. Questions and discussions regarding stigma, racism, discrimination and structural inequality may cause anxiety, anger, suspicion, or other emotions. While we expect our sample to be predominantly African American, there will be some White and Latino participants as well and talking about racism in the group will elicit strong emotions. Differences among group members have the potential to harm or cause discomfort for a participant or to revive psychological dynamics that could threaten to renew old conflicts.

13B. Describe the steps that will be taken to minimize the risks listed above.

To avoid possible violations of confidentiality, project staff are trained to carefully follow detailed procedures designed to assure that no information about any participant (or others they may mention) will be given to anyone other than members of the research staff included in the IRB protocol. Every member of the research team and all NCCB and ICCB members will be required to undergo human subject protection training and provide a certificate of completion to the IRB prior to any contact with human participants. Standards of confidentiality include the use of code numbers and code names for participants and other individuals they may mention. The only place participants' names or other identifying information will appear is on informed consent forms and locator forms that are password protected in RedCap, the software used in the study. This identifying information is used for follow-up interviews after the baseline, to remind participants of Critical Dialogue group sessions if they are randomized to that condition and to locate participants if we are unable to reach them. Consent forms will be stored in locked filing cabinets at CBHC, separate from any data. [name], the Project Principal Investigator at CBHC, will retain the keys to the filing cabinets at each location. Only outreach staff, [name], [name], and the group facilitators will have access to the identifying information.

The electronic files generated through data collection will be identified by code numbers only and kept in password-protected and HIPAA-compliant devices/cloud, separate from identifying information and available only to project staff. This helps to ensure that no identifying information will be disclosed in the unlikely event that computerized data are stolen or otherwise seen by unauthorized persons. All identifying electronic data will be destroyed immediately after data collection is completed. Signed consent forms and audio recordings will be kept for 3 years after study completion. De-identified

electronic data will be kept indefinitely. Study participants may ask at any time to have recordings of their interview destroyed by calling/e-mailing one of the Principal Investigators at the numbers provided in the informed consent forms.

Participants will be protected by a Certificate of Confidentiality issued by the NIH. NIH issues COCs automatically upon funding approval. Under terms of the Certificate, the researchers cannot be forced to disclose information that may identify a participant, even by a court subpoena, in any federal, state, or local civil, criminal, administrative, legislative, or other proceedings. However, the Certificate cannot be used to resist a demand from United States Government personnel for information that is used for auditing or evaluation of federally funded projects or for information that must be disclosed in order to meet the requirements of the federal Food and Drug Administration (FDA). Researchers may also disclose the identity of participants who report intentions to harm themselves or others or if researchers have knowledge those participants are abusing children or elderly persons

Our interviewers are trained to watch participants carefully and will stop questioning if an individual appears uneasy. At every interview, participants will be informed that they may ask the interviewer to stop if they are feeling uncomfortable. Referrals to counselors are available if participants wish and trained clinical counselors are available at CBHC in the event that someone may need immediate assistance, whether it is during data collection or during the intervention sessions. The Critical Dialogue is an intervention developed by [name] and the NCCB, to ensure that the group discussions happen in a safe way, where everyone is encouraged to challenge their own assumptions by analyzing the evidence they have that supports or challenges their positions. This starts with operational components where the intervention is clearly described so that people know what to expect, and ground rules are collaboratively created and enforced during group discussions. In preliminary research on the intervention, there were many instances where the critical questions posed led to a heated dialogue where people were able to express their conflicting views while respecting each other and considering the possibility of changing their points of view. [name] will train a doctoral level social work research assistant to facilitate the groups. The RA has a great deal of experience facilitating groups dealing with these sensitive topics and with this marginalized population. In the unlikely event a discussion escalates to the point that it may challenge the safety of the group, there is an emergency protocol in place where trained clinical staff and security can intervene and deflect potential violence or stabilize medical emergencies. During the development and testing stages of the intervention, with close to 700 participants, no adverse events occurred as a result of critical dialogue participation.

The IRBs of the collaborating institutions, the NJCRI, CBHC, and the University of Michigan, will defer oversight to the UIUC IRB. As the applicant agency, the University of Illinois Urbana-Champaign will ensure that all institutions adhere to IRB monitoring and will keep annual certificates from each institution on file. UIUC will execute an Institutional Review Board (IRB)/Independent Ethics Committee (IEC) Authorization Agreement with all other agencies. The Officials signing this Agreement will thereby

agree that their institutions may rely on the IRB of UIUC as the designated IRB for review and continuing oversight of its human subjects research described for this project.

[name], [name], [name], and [name] will be available by phone at all times in case an emergency occurs. Any adverse event will be reported to the IRB and funding agency within 24 hours. Through our ICCB collaboration, we have excellent relationships with the community, including community members and agencies that we can mobilize in case the need arises (e.g., access to detox and emergency services, legal support clinics).

Finally, the research team and the clinical team will engage in weekly project meetings to receive ongoing training, discuss the progress of the study and identify and address any potential issues.

13C. Indicate the risk level.

No more than minimal risk

(The probability and magnitude of harm or discomfort anticipated for participation in the proposed research are not greater in and of themselves than those ordinarily encountered in daily life or during the performance of routine physical or psychological examinations or tests).

More than minimal risk (answer 13D)

13D. If you checked that the research is more than minimal risk, describe the provisions for monitoring the data to ensure the safety of subjects, such as who will monitor data and how often, what criteria will be used to stop the research, etc.

The MPIs will oversee data management, including data storage, security, random assignment and quality assurance procedures, REDCap, software and hardware, and will ensure that all staff adheres to Human Subjects guidelines. Data management activities and procedures, including data confidentiality, will employ an electronic data management system to enhance efficiency, security and integrity of study data. The ICCB will also be updated during meetings on data management and adherence to IRB protocol.

Additionally, integrity assessments will be conducted, which include: (1) a checklist completed by facilitators at the end of each intervention session to list the activities discussed in each session and participant attendance; (2) exit interview. The NCCB and ICCB will review preliminary findings presented by the MPIs on a bi-monthly basis to address any potential adverse reactions that may occur and any safety concerns that may arise. If any participants are found to be unresponsive to the intervention during the course of the study, the Board will discuss the case and the participant may be terminated from the study and referred to relevant services in the community. The MPIs will meet bi-weekly with study staff to review study protocol adherence and address any potential problems. MPI [name] will have weekly supervision meetings with intervention facilitators to review results from fidelity ratings and address any potential deviance from intervention protocols.

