All participants will be asked to complete follow ups 4 and 5. We will collect screening data via phone, and in-person baseline assessment, and follow- ups at 2, 5, 12 and 24 weeks follow-ups. Participants will be encouraged to complete the surveys online, using their phones, a tablet, or computer. They can also request to meet the outreach workers at CBHC or a public place to complete the data collection using a study tablet, as long as they agree to adhere to the most current public health recommendations (e.g., social distancing).

After each assessment, participants will be asked to provide extensive locator information, on forms used for the parent study, including formal and informal contacts who can reach the participant in a variety of contingencies. During the follow-up period, outreach workers will maintain monthly contact with participants by mail or phone and will update locator information. Randomization and data collection will be done online using Redcap. We will voice record all Critical Dialogue sessions with participants' consent and will randomly select 20% of them for analysis.

The research team will randomly select 35 participants at each site who decline to be tested for COVID-19 and invite each of them to complete an in-depth, one-on-one, qualitative interview lasting about 30 minutes. After providing written informed consent, participants will be assigned code names and asked to talk about their experiences with the intervention, barriers they faced to testing and adhering to public health guidelines, and their ideas about how to address these barriers. The interviews will be digitally voice-recorded, transcribed and entered into Atlas.ti for storage and analysis. Transcripts and Atlas.ti files will be identified only by code name.

Additionally, data from the COVID-19 NJ Study will be analyzed. These data include the exact same surveys as the data being collected in Illinois. The data is being collected under NJCRI's IRB number. UIUC deferred to the NJCRI IRB because all the NJ data is being collected there. The NJ data will be de-identified and shared electronically by the NJ research assistant using Box. The NJ data will then be merged with the Illinois data for analysis.

The figure below illustrates the study design:

COVID-19 Testing

Section 8. PERFORMANCE SITES TO INCLUDE INTERNATIONAL, SCHOOL, AND COLLABORATIVE STUDIES

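### The adverse-event definition leaves out confidentiality breaches and perhaps distress, and with no scheduled harms question described, capture can differ by randomised arm

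*Protocol*

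**What the plan says.** The adverse-event text under Protocol Section 8 places the duty on staff: "Any research staff member who learns of an adverse event is responsible for reporting the event to the Principal Investigators (PI"). An AE is "any untoward medical occurrence that may present itself during treatment or administration of an intervention", whether or not the intervention caused it. The serious category is also medical: "Serious adverse events (SAEs) are defined as any medical occurrence that results in death", followed by the other criteria for seriousness. The same text commits that "adverse events (AEs) occurring during the course of the study will be collected, documented, and reported to the PIs" and has an investigator look through the AE forms every week. It does not say what is asked, when, or by whom. Section 13F sends SAEs to the DSMB, and has AEs kept in a database and reviewed at each DSMB meeting.

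Section 13A states: "The main potential risks of this study include inadvertent violation of confidentiality and emotional distress on the part of participants". For distress during data collection, Section 13B (as does 9C) relies on observation: "Our interviewers are trained to watch participants carefully and will stop questioning if an individual appears uneasy". On how surveys are done, Section 7F says: "Participants will be encouraged to complete the surveys online, using their phones, a tablet, or computer". Meeting an outreach worker is an option.

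Staff contact by intervention (7E, 7F):

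- Navigation: at least one session of up to 30 minutes, with more as agreed.
- Brief Counseling: a 15-minute session with a clinician.
- Critical Dialogue: one facilitated group session.
- Brochure: sent automatically by e-mail.

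Section 17A lists adverse events among the results to be posted. The SAP contains no AE analysis.

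**The concern.** The harms the investigators expect are not clearly the harms the system is built to record. If the definition is followed as written, the DSMB could see an empty AE table although a breach, or a session stopped by distress, had occurred.

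Capture is the second issue. Where no common question is asked, an event is recorded when a staff member hears of it, and randomisation sets how much live contact a participant has. A higher count under Navigation or Critical Dialogue could mean more harm or only more listening. A low count under Brochure could mean safety or silence.

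**Working it through.** There is no AE rate, detection rate or safety power in the documents, so there is no figure to reproduce. The check sets the sections side by side and then adds a labelled illustration.

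**1. Definition against named risks.** A confidentiality breach is not a medical occurrence, so it is neither an AE nor an SAE under Section 8. Severe distress could qualify; distress that merely stops a survey or session need not. No available section gives a breach, or such lesser distress, a recording route to the DSMB.

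**2. Is the same harms question asked in every arm?**

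| Route | What is described | Equal harms inquiry? |
|---|---|---|
| Staff report, AE forms, weekly review, database (Section 8, 13F) | Handling once an event is known | None described |
| Surveys (7B, 7F) | Same schedule in all arms, mainly online; content is in attachments not available here | Unknown |
| Monthly contact (7F) | Mail or phone, to update locator details | None described |
| CBHC testing (7F) | Outreach worker handles the sample and gives the result | Open to all arms; no harms question described |
| Session checklist, exit interview (13D) | Checklist covers activities and attendance, where a session exists | None described |
| Interviewer observation (9C, 13B) | Works only when staff are present; no instruction to record | No |
| Community board review (13D; SAP, Interim analyses) | Adverse reactions and safety concerns | Acts only on what was captured |

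**3. How many have no live intervention session?** The Illinois sample is 548 (11C), and the SAP gives equal probabilities at both stages. Brochure first: 548 × 1/2 = 274. Brochure again: 274 × 1/2 = 137. This counts by assignment and assumes that everyone is re-randomised. It is an upper figure because Section 7F later invites those still untested at follow-up 3 to a Critical Dialogue session.

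**4. Illustration (all rates assumed).** Let both first-stage arms have the same true AE rate p, with n = 274 each, and let staff hear of fractions d1 and d2 of events. Recorded events are n × p × d, and the expected recorded ratio is d1/d2. The last column is the chance of a nominally significant false difference (two-sided 5% test of two proportions, normal approximation). At p = 5% there are 274 × 0.05 = 13.7 true events per arm:

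| d1 v d2 | Recorded events | Ratio | False-signal chance |
|---|---|---|---|
| 0.6 v 0.6 | 8.2 v 8.2 | 1.0 | 5% (nominal) |
| 0.6 v 0.4 | 8.2 v 5.5 | 1.5 | about 11% |
| 0.8 v 0.4 | 11.0 v 5.5 | 2.0 | about 28% |
| 0.9 v 0.3 | 12.3 v 4.1 | 3.0 | about 54% |

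For p from 2% to 10%, the last column runs from about 7% to about 84% over the three unequal rows. The approximation is rough at the smallest counts.

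These rows hold the detection gap constant across each whole arm, which is generous to the concern. Half of the Brochure-first arm is assigned to a live session after the first follow-up. If those participants are then heard at 0.8 while the rest stay at 0.4, the arm average is (0.4 + 0.8)/2 = 0.6. Against 0.8, the ratio falls to 0.8/0.6 = 1.33, or 4% v 3% recorded at p = 5%.

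**The case against.** The strongest reply is that the plan has more safety machinery than the reporting sentence suggests: a general commitment to collect and document AEs, AE forms, weekly review, a database seen by the DSMB, and community boards that consider adverse reactions and safety concerns without limiting them to medical ones. That is right, and it rules out several stronger readings.

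- *A reader might infer that events are logged only by chance.* The documents do not support this. The surveys are unseen attachments, and Section 16D mentions a separate DSMP, so a solicited item cannot be excluded. What can be said is that no scheduled inquiry is described in the available text.
- *A reader might infer that the documents contradict themselves on how risks are watched.* They do not. Naming risks in 13A and using a medical AE definition in Section 8 leaves a gap. Watching participants at interviews is compatible with encouraging online surveys.
- *A reader might infer that distress is excluded altogether.* Section 13B speaks of adverse events in connection with Critical Dialogue, so the team may count some distress. The gap is clear for breaches and partial for distress.
- *A reader might infer that capture does differ by arm.* All arms share the survey schedule, monthly contact and access to CBHC testing, so it can differ; whether it does is not shown.

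Two further points carry weight. The SAP plans no AE comparison by arm, so any bias would lie in the posted counts rather than in a planned test. In the group of 137, an assumed 5% rate with 80% v 40% detection is 137 × 0.04 = 5.5 v 137 × 0.02 = 2.7 events, too few to read much into. Neither point gives breaches a route to the DSMB or makes the posted counts comparable.

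**Conclusion.** The point holds as a gap that should be closed. As written, a confidentiality breach is outside the AE and SAE definitions, and distress short of a medical event may be, so DSMB review of AEs can miss either of the main risks named in 13A. Because live contact depends on arm and no equal harms inquiry is described, posted AE counts may not be comparable between arms.

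The size is unknown. The recorded ratios of 1.33 to 3.0 rest entirely on assumed detection rates and equal true rates. The only figure that follows from the documents is the upper count of about 137 Illinois participants with no live intervention session, by assignment. The verdict also assumes that the survey attachments contain no harms item; if they do, the second part largely falls away and the definition gap remains.

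A related inconsistency needs reconciling. Section 13B has any adverse event reported to the IRB and funder within 24 hours, while Section 8 and 13F give 48 hours for serious events. An SAE is an adverse event, so both limits apply to it.

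**What to change.** First check the survey attachments for an existing harms item. Then amend the adverse-event text under Section 8:

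1. Name as reportable study events on the AE form (a) a confidentiality breach and (b) distress that stopped a survey or session or led to a counsellor referral. Have the DSMB review them with the AEs.
2. Put one identical harms and distress item in every follow-up survey in all arms, flagged through REDCap to existing study staff. If the New Jersey survey cannot change, use an Illinois module.
3. Tabulate solicited events by arm, separately from events that staff learned of in other ways.
4. Reconcile the 24-hour and 48-hour reporting statements.

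If the common item equalises detection, the expected recorded ratio under equal true rates is 1.0.

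The cost is one survey item with a flag, new wording on the AE form and a short amendment. Interventions and randomisation do not change. The downsides are more minor events to review and an item that may be missing from the New Jersey data, which would break the present match between the two surveys.
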